6.2.1 Screening Evaluation

Consenting Procedure

Prior to enrollment, during in-person screening visit (#1) the PI or Co-Is will obtain IRB-approved informed consent from subjects. The consent form will be reviewed with each subject prior to signing this consent form. All subjects will be offered an opportunity to discuss the study with their primary physicians and family members prior to signing the consent form.

This will be followed by neuropsychiatric and physical examinations, and laboratory tests (2 1/2 hours). Though eligibility will be assessed again at baseline, participation may be terminated if the subject stops meeting entry criteria. No subject will be asked to discontinue effective antidepressant medications or psychotherapy.

Screening (Visits 1-3)

All subjects will receive an initial *medical evaluation* including a complete physical examination with neurological and neuropsychiatric examinations, electrocardiogram (ECG) (for potential cardiac complaints), and laboratory testing to rule out new-onset medical illnesses that could account for behavioral and cognitive symptoms. *All abnormal physical or laboratory findings will be reported to subjects' primary physicians with subject's consent. If abnormal physical or laboratory results are considered responsible for depression, the subject will be excluded from participation.* All subjects will be interviewed about their recent history of psychiatric and medical illnesses, psychosocial stressors, current medications and health status. In addition, vital signs including pulse rate, systolic blood pressure, and body weight will be obtained at each visit. The UKU Side Effect Rating Scale,¹⁰⁹ a comprehensive rating scale for monitoring adverse events in

clinical trials, will also be completed at all visits except screening.

Dementia. We will screen for possible incipient dementia to exclude participants. This will include reviewing an extensive history and mental status exam together with corroborating information with regard to functional skills. A MMSE score of ≤ 24 , the clinical dementia rating score of CDR score >0.5 or an established dementia diagnosis will mandate exclusion. The evaluation for dementia includes: 1) an interview by a psychiatric nurse to identify physical and cognitive limitations; 2) a standard battery of hematologic studies; 3) neurological examination (UPDRS); 3) neuropsychological examination (detailed below); and 4) psychiatric evaluation (SCID), as detailed above. Adjudication of dementia is based on DSM-5 criteria.^{110,111} At the consensus conference, additional information will be reviewed (e.g., family history, drug use).¹¹² *We will use performances between -1.5 and -2 (SD) below age and education norms on one of two memory tests from our cognitive battery to establish cut-offs according to a widely accepted practice for the diagnosis of dementia.*

Blood Sample. **Blood samples will be collected for the RNA and telomerase analyses at screening (visits 1-3) and 12 weeks post-randomization (or early termination).** A sample of 10ml of blood will be collected and it will be processed by the Core Laboratories of UCLA Department of Human Genetics.

Neuropsychological Assessments: Neuropsychological tests will be administered **at screening (visits 1-3), week 12 (visits 10-11), and 6, 12, and 14 months (visits 14-19)** (See 6.2 for descriptions of evaluations).

MRI Imaging Biomarkers: Imaging data will be acquired from 110 subjects (55 per group) at baseline, at 12-weeks post-randomization (or for early termination), and at 12-months post-randomization on a Siemens Prisma system using a 32-channel head coil. Each scanning session will last 60 minutes and include 1) a T1-weighted multi-echo MPRAGE (MEMPR) sequence with real time motion tracking and correction for the examination of brain structure; 2) a bandwidth matched T2-space sequence for detection and quantification of WMHs and CSF; and 3) three separate BOLD EPI sequences for the acquisition of rs- and task-related fMRI data used for the examination of emotional and working memory processing and functional connectivity. In addition, a 3-plane localizer and a non-BOLD EPI sequence co-planar to the fMRI data for cross-modal image registration will be acquired. The morphometry sequences are optimized for determining brain tissue contrast with reduced distortion.¹¹³

Table 5. fMRI sequences

3D T1 MEMPAGE	TEs/TR= 1.74, 3.6, 5.46, 7.32/2530 ms, TI=1260 ms, FA=7, FOV=256 mm, matrix=256x192, voxel size=1 mm ³ , run time: 8:14 min.
3D T2 SPACE	TE/TR= 425/3200 ms, FA='T2 var', FOV=256 mm, matrix=256x192, voxel size=1 mm ³ , ETL=769, 2xGRAPPA, run time: 4:43 min.
fMRI (emotion and working memory)	TE/TR=25/2500 ms, FA=80°, matrix 64x64, FOV=20 cm, 34 axial slices, slice thickness 3 mm, .75-mm gap, run time: ~6 min each.
Resting state fMRI	TE/TR=30/2000 ms, FA=80°, matrix 64x64, FOV=20 cm, 34 axial slices, slice thickness 3 mm, .75-mm gap, run time: 8 min.

Functional Imaging: To address our hypotheses that TCC versus HEW will result in greater activation in right VLPFC and the amygdala during emotional processing (Hypothesis 2a) and greater working memory-related activation in the DLPFC and other network regions (Hypothesis 2b) we will employ two widely-validated brain activation tasks that probe emotional processing and working memory function (see preliminary studies). Similarly, analysis of rs-fMRI data will

determine whether TCC associates with plasticity in brain network activity. **Faces Affect Labeling Task.** We will use a previously detailed Faces/Shapes brain activation task shown to produce robust and reliable activations in amygdala and PFC regions during emotion processing, making this paradigm particularly appropriate for longitudinal investigation.^{114,115,116} In brief, during this task participants are required to match emotions (activating the amygdala and VLPFC), label emotions (activating the VLPFC) or match forms (a control condition) while presented with faces showing different emotional expressions or geometric shapes [Fig.1]. Since subjects are not asked to attend or regulate their affect, brain activation is more closely linked with affective reactivity, rather than with affect perception.¹¹⁶ The task includes 5 blocks of the control shape-matching task interleaved with 4 blocks of the experimental faces condition. Button press responses monitor accuracy and reaction time. Though some mixed findings exist, previous studies, and our pilot data suggest that implicated VLPFC hypoactivity, as well as task-related activation of the amygdala may vary with response to treatment and clinical state.¹¹⁷ **Working Memory Task.** We will use a well-established 2-back version of the n-back task detailed in Townsend et al.,¹¹⁸ to elicit neural activation linked with working memory. This task consists of two blocked conditions with a 20 s resting condition interleaved between conditions. In the experimental 2-back condition subjects track letter sequences and press a button when they detect a letter that appeared 2 positions back. In the control 0-back condition, subjects will press a button every time the letter "X" appears on-screen. Button presses record accuracy and response time. This version of the n-back has been employed in our laboratory to show significant reductions in activation of the DLPFC and posterior parietal cortex across mood state in bipolar subjects compared to controls¹¹⁸ as well increased activation in association with clinical response in LLD (see preliminary studies). **Resting State-fMRI:** During acquisition of BOLD rs-fMRI data, subjects will be asked to remain awake with their eyes closed. Though resting state connectivity is highly reproducible over time in healthy subjects¹¹⁹, experience-based neural plasticity in resting state connectivity has been shown to occur over periods as short as 2-9 days.¹²⁰ Recent research points to significant changes in DLPFC and cingulate connectivity in association with ECT.^{53,54}

Preprocessing and Analysis: *Preprocessing of all fMRI data* will follow similar workflows executed in the LONI pipeline environment, where standard and state-of-the-art image analysis programs interact seamlessly in a parallelized supercomputing environment. Specifically, preprocessing steps incorporating FSL (www.fmrib.ox.ac.uk/fsl) and custom processing modules, will include: a) removal of non-brain tissue; b) rigid-body head motion correction; c) spatial smoothing (5-6 mm FWHM); d) denoising and high pass filtering using FSL's MELODIC; and d) co-registration of the BOLD and T1 images using the matched bandwidth EPI images for intermediate registration. First-level analysis will include the modeling of activation between task conditions (e.g. match emotion vs. shapes; or 0-back versus 2-back). Temporal derivatives and the 6 motion parameters will be included as covariates of no interest to improve statistical sensitivity. Second-level (fixed effects) and third-level (mixed effects) analyses will average runs within subjects and across groups respectively for subsequent comparisons between the treatment groups. **Longitudinal analysis:** In addition to subtracting changes in activation between baseline and follow-up scans within individuals for subsequent group comparisons, we will represent fMRI maps as statistical change maps in time, with each voxel representing a smooth change in magnitude (positive or negative) from the baseline dataset. These maps will be presented against the structural template, to determine the effects of structural change, functional change, and their interaction. One sample t-tests will determine if activation for each individual changes significantly over time. **Task-related connectivity analysis:** To investigate effective "functional" connectivity, we will perform a psychophysiological interaction (PPI) analysis,¹²¹ which determines differences in task-dependent functional connectivity between regions-of-interest (ROIs). We will investigate the effect of the emotion-labeling task relative to the shape control, using voxels in the amygdala as "seeds" and voxels in the PFC as the "target." Group-level FSL FEAT analyses will determine voxels throughout the brain showing significantly correlated task-

dependent activity with the ROI. Regressors include the physiological variable (e.g., amygdala activity), the psychological variable (emotion vs. shape), and their interaction. Higher-level analyses will determine the degree of functional coupling among treatment groups. **Resting state analysis:** After applying preprocessing steps similar to those described above, widely documented independent components analysis (ICA),^{51,122} using FSL's MELODIC, will estimate the optimal number of components for each subject and will remove components representing artifacts. After low pass filtering (0.1-0.01 Hz) and transformation into atlas space, the best-fit DMN component for a subject will be selected for higher-level group analysis. We will explore components of other networks. We will also examine voxel correlation within particular networks in follow-up analyses of ROIs^{49,51,123} Changes in functional connectivity will be quantified by comparing Fisher z-transformed correlation coefficients between ROIs. **Structural Imaging:** Structural image analysis will incorporate methods refined and validated by project co-investigators and include: 1) volumetric analysis using automated and manual segmentation, 2) refined shape/surface structure analyses and 3) tensor based morphometry (TBM) analysis using Jacobian determinants to quantitatively map voxel-level morphometric change throughout the brain. In brief, widely used Freesurfer (<http://surfer.nmr.mgh.harvard.edu/>) processing streams that include a) correction for magnetic field inhomogeneities; b) removal of non-brain tissue; c) tissue segmentation; d) separation of the hemispheres and subcortical structures; e) extraction of the white/gray and pial cortical surface and f) initial segmentation of cortical and subcortical ROIs (with manual correction of errors) will be used to estimate regional tissue volumes for comparison across treatment groups and time. These analyses will be followed by more refined morphometric analysis to reveal local changes in the shape/surface structure of subcortical ROIs as informed by the volumetric and TBM results (see below). Procedures include the use of surface-based mesh modeling and skeletonization methods that have been used to assess extremely local changes in the morphology of the amygdala, striatum and hippocampus in several clinical groups including LLD and across time in our prior studies.¹²⁴⁻¹²⁶ Finally, we will employ TBM methods that are shown as highly sensitive for detecting subtle changes in brain morphometry associated with maturation/aging or disease,^{117,126-131} to examine both global and local changes in brain tissue structure across treatments and time. **WM Hyperintensities (WMH):** The 3D T2-space images will be used to visualize WMHs by employing a semi-automated WMH identifier.¹³² Briefly, WMH burden will be assessed based on the signal intensities of co-registered 3D MEMPR and T2-SPACE images, and population statistics on the spatial distribution and neighborhood structure of WM lesions. With every unit increase in WM burden, we will estimate % reduction in local brain tissue volume. GLM and multiple regression analyses will determine links between WM burden and clinical measures in each group and may be controlled.

Blood samples and peripheral biomarkers.

Genetic testing. Participation in the genetic portion of the study is voluntary. If subjects are deemed ineligible, they will not undergo genetic testing.

DNA and gene expression: Genomic DNA will be extracted from whole blood and isolated using a Wizard Genomics DNA Purification Kit (Promega Corporation, Madison, WI, USA), and determined with 0.7 % agarose gel (Beutler et al., 1990) according to the standard protocol.

RNA and microarray analyses: RNA will be extracted from whole blood and isolated using a Wizard Genomics DNA Purification Kit (Promega Corporation, Madison, WI, USA), and determined with 0.7 % agarose gel (Beutler et al., 1990) according to the standard protocol.

Telomerase and NFκB peripheral cytokine collection: Standard Operating Procedures (SOP): The procedures that will be taken to protect the confidentiality of the subjects who donate samples. Telomerase and NFκB samples will be obtained once at baseline and once at week 12 to evaluate telomerase activity in response to the antidepressant intervention. Telomerase and NFκB samples will be collected concurrently with the other investigational labs, so no additional needlestick is necessary for this test. Subjects will not be asked to fast before the draw and will

not receive any additional monetary compensation for this portion of the research. 10ml of blood will be drawn into one green Heparin tube yielding 50-150 micrograms of the specimen. After collection, telomerase samples will be labeled with the study code, date and time of collection, and an identification number assigned to each subject by the PI or the study coordinator. This identification number will be the only link between the samples and the subjects and will only be accessible to the PI and to certified members of the research team. This information will be stored in an electronic log that is password protected. No other personal identifiers will be listed on the specimen. The collection will be performed at the UCLA Clinical and Translational Research Center (CTRC).

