For Aim 2 of detecting group differences in imaging biomarkers, our design with complete data on 55 subjects within each arm at the end of treatment will have 80% power at significance level $\alpha=0.05$ for detecting a group difference between any two arms of $d = 0.53$ SDs. Our preliminary studies reported in Section 1.1.2 for antidepressant treatment response, found effect sizes of $d = 0.57$ for changes in BOLD response in bilateral occipital cortex and right VLPFC (faces affective reactivity task), in BOLD response in left DLPFC, premotor and bilateral posterior parietal regions (N-Back task) between baseline and end of treatment at 16 weeks. If TCC changes in brain function resemble those induced by psychopharmacological agents, our design will have enough power to detect group differences in imaging biomarkers.

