Aim 2. Hypothesis 2a, b: Primary analysis: Similar to Aim 1, the primary outcomes of DMN connectivity in rs-fMRI and BOLD activation during the mood task in the anterior cingulate will be modeled with a GLMM model with treatment group and time as main effects, along with their two-way interaction. Significant interactions would suggest differential trajectories over time for activation and connectivity outcomes in the two treatment groups. Primary analysis will assess treatment effects at 12 weeks in the primary outcomes. Sensitivity to missing data will be studied as explained in detail in Aim 1. The outcomes of DMN connectivity in rs-fMRI and BOLD activation will be treated as co-primary endpoints and further we will carefully examine the effect size of each co-primary endpoint to ensure clinically meaningful treatment effect.

Secondary analysis: Secondary measures for Aim 2 will be BOLD activation during the cognitive task in hippocampus. Secondary analysis will include assessment of treatment maintenance effects on the primary and secondary outcomes and of treatment effects during treatment in the secondary outcome of BOLD activation during the cognitive task in hippocampus.

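### The DMN connectivity co-primary has two non-equivalent derivations, and the plan does not say which one enters the Aim 2 model

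*Combined protocol and SAP*

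**What the plan says.** Section 6.2.1, under Resting state analysis, describes two routes to a DMN measure.

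- **Component route.** ICA in MELODIC "will estimate the optimal number of components for each subject and will remove components representing artifacts". After filtering and transformation to atlas space, "the best-fit DMN component for a subject will be selected for higher-level group analysis". No template, fit index, threshold, tie rule or fixed number of components is given, and there is no group decomposition or projection of a common map onto each scan.
- **Region route.** "We will also examine voxel correlation within particular networks in follow-up analyses of ROIs", and then "Changes in functional connectivity will be quantified by comparing Fisher z-transformed correlation coefficients between ROIs". The regions are not listed. The first of these sentences places region work in follow-up; the second reads as the general rule for measuring change.

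Section 9.6, Aim 2, gives the endpoint its status: "The outcomes of DMN connectivity in rs-fMRI and BOLD activation will be treated as co-primary endpoints". It is analysed in a mixed model with group, time and their interaction, and "Primary analysis will assess treatment effects at 12 weeks in the primary outcomes". Neither the opening of Section 9.6 nor its Aim 2 text says which resting-state value is the dependent variable. Under Hypothesis 2c, change in the same quantity is also the posited mediator, as an exploratory analysis.

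Section 9.2 states the power for imaging biomarkers: "our design with complete data on 55 subjects within each arm at the end of treatment will have 80% power" for a difference of 0.53 SD at alpha 0.05.

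**The concern.** The mixed model needs one number per scan, with the same meaning in every subject and at every visit. The component route does not ensure this. A decomposition with more components can spread over several maps what one with fewer components keeps in a single map. Picking the best-fitting map may then return more of the network in one subject and less in another. An arm difference in that score would partly reflect how each decomposition fell.

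The region route does not have this weakness if the regions are fixed in advance, but they are not named. The two routes can give different answers from the same scans. With neither designated, the co-primary could be settled after the results are known. At stake are one of the two Aim 2 co-primaries and the exploratory mediation analysis that uses it.

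**Working it through.** **1. The two routes side by side**

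| | Component route | Region route |
|---|---|---|
| Unit measured | One selected ICA map per subject | Correlation between pairs of regions |
| Same definition for all subjects? | Not assured: number of components is subject-specific, pick rule unstated | Yes, if regions are fixed in advance; none are listed |
| Role stated in 6.2.1 | Sent to the higher-level group analysis | Introduced as follow-up, then given as the way change is quantified |
| Named in 9.6 as the co-primary? | No | No |

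The text speaks of components for each subject. It does not say whether the ICA is run on each scan or once over all of a subject's scans. If per scan, correspondence between visits is not assured either. If pooled, one map results per subject, and the step that turns it into a value per visit is missing. Correspondence between subjects is unassured in both cases.

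**2. The plan's own power figure**

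Inputs from Section 9.2: n = 55 per arm, d = 0.53, alpha = 0.05. Two-sided testing is assumed because sidedness is not stated.

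Power ≈ Φ(d·√(n/2) − 1.960)
= Φ(0.53 × 5.244 − 1.960)
= Φ(0.819) = 0.794.

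The noncentral t gives 0.787. A one-sided test would give 0.872, which does not match. The detectable difference is (1.960 + 0.842) × √(2/55) = 0.534. The stated 80% therefore reproduces as a two-sided, two-sample comparison.

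**3. What noise in the measure could do (assumed values only)**

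The documents give no reliability for a DMN measure. Suppose 0.53 is the effect on an error-free measure. Then observed d = 0.53 × √reliability.

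| Assumed reliability | Observed d | Power, 55 per arm | n per arm for 80% |
|---|---|---|---|
| 1.0 | 0.53 | 79% | 56 |
| 0.9 | 0.50 | 75% | 63 |
| 0.8 | 0.47 | 70% | 70 |
| 0.7 | 0.44 | 64% | 80 |
| 0.5 | 0.37 | 50% | 112 |

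Alternatively, suppose a share m of subjects have a selected component that carries no treatment effect, so that observed d = 0.53 × (1 − m). For m = 5%, 10% and 20%, power is 75%, 71% and 60%.

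If 0.53 is already in SDs of the measure as observed, ordinary measurement noise is inside the figure and power stays at 79%. A noisier measure then requires a larger underlying effect to reach the same observed d: 0.534/√0.8 = 0.60 at reliability 0.8, and 0.534/√0.5 = 0.76 at 0.5.

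The supporting effect in Section 9.2, d = 0.57, is a change in task BOLD response on antidepressant treatment. It is not evidence about DMN connectivity.

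**4. What an open choice could do**

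Suppose both derivations are tested at 0.05 and the more favourable is reported. The chance of a false positive on this endpoint lies between 5% (the two always agree) and 1 − 0.95² = 9.75% (independent). Two measures from the same scans would be correlated, so the true value lies between these limits.

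**The case against.** The strongest reply is that the plan already says how change is measured. Aim 2 is a contrast in change, and the Fisher z sentence can be read as settling it, with ICA serving only to clean the data and display the network. That reading is possible. It does not close the gap: the selected component is expressly sent to the group analysis, region work is introduced as follow-up, no regions are listed, and Section 9.6 adopts neither.

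A reader might infer more than the text supports, in three ways:

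- **That the measured network differs between visits.** The text does not say so, because it is silent on per-scan or pooled decomposition.
- **That the Aim 2 contrast is diluted.** The documents give neither a reliability nor a rate of mismatched components, so this is a possibility of unknown size. A pick that tracked treatment-related change could also bias the contrast in either direction.
- **That the 80% power will not be met.** The figure reproduces, and it stands if 0.53 is in observed SDs.

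The weight of the point is also limited. Section 1.2 lists Aim 2 among the secondary objectives, and Section 9.5.1 makes HAMD change the primary outcome. Section 6.2.3 blinds the statisticians and the principal investigator and codes the groups 1 and 2. That lessens the risk of a steered choice. It does not remove it, since the size of a difference between coded groups is visible without knowing which group is which. Finally, the cited ICA references may set out a selection procedure, but they cannot be consulted here and the plan does not say that they do.

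**Conclusion.** The point holds as a gap in specification. Section 6.2.1 offers two non-equivalent derivations of one co-primary, and Section 9.6 does not choose. On the component route, as written, nothing assures that the same network is scored in every subject. The possible results are added noise in the week-12 contrast and a choice left open until results are seen.

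The size of the noise cannot be derived from the documents. The range of 75% to 50% power rests on assumed reliabilities of 0.9 to 0.5 and on treating 0.53 as an error-free effect. The inflation of up to 9.75% assumes that both derivations are tested and the better one is kept. No stated figure is shown to be wrong. This is a cheap improvement, not a fault that undermines the trial.

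**What to change.** Before unblinding, state in Section 6.2.1 (Resting state analysis) and Section 9.6 (Aim 2) that the DMN co-primary is one scalar per scan, with the same definition for every subject and visit, computed blind to arm.

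- **Simplest choice:** the Fisher z measure that the plan already names, averaged over all pairs in a listed, a priori set of DMN nodes.
- **Acceptable alternative, if designated in advance:** regress every scan on one common DMN template taken from a pooled, arm-blind decomposition with a fixed number of components.
- Use subject-level ICA only to remove artifacts, and report any best-fit component analysis as secondary.
- Use the same scalar for the mediation analysis under Hypothesis 2c.
- Say explicitly that those who process the scans are blind to arm. Section 6.2.3 points that way but does not name them.

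The cost is a change of wording and some reprocessing of scans that the trial collects anyway; no new data are needed. The downside is that a common definition fits individual anatomy slightly less closely.

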1.2 Secondary Objectives

Aim 2. To test whether 12 weeks of **TCC** compared to **HEW** training alter neural regulation of affect during an fMRI affect labeling task and functional connectivity in older adults with depressive symptoms. Imaging biomarkers will predict/moderate treatment response.

Hypothesis 2a: Compared to HEW, TCC will lead to improved functional connectivity in the Default Mode Network as measured with resting state (rs-) fMRI;

Hypothesis 2b: Compared to **HEW**, **TCC** will result in greater activation in the anterior cingulate;

Hypothesis 2c: Imaging biomarkers (hippocampal and anterior cingulate volume, white matter hyperintensity and DMN connectivity) will moderate and predict 1) rate of improvement in symptoms and function; and 2) improvement in cognitive performance.

Aim 3. To examine whether older depressed participants with MCI (LLD+MCI) differ in their cognitive trajectory and neural circuitry compared to older depressed participants without MCI (LLD-MCI) at extended follow-up of 6 and 12 months.

Hypothesis 3a: We hypothesize that changes in episodic memory and executive function will be greater in those with LLD+MCI than in those with LLD-MCI.

Hypothesis 3b: We hypothesize that changes in the default mode/hippocampal-frontal network and in the executive-control and cortico-limbic circuitry will be greater in those with LLD+MCI than in those with LLD-MCI.

Aim 4. *To examine whether greater degradation of neural circuitry is associated with greater cognitive decline.*

Hypothesis 4: We hypothesize that changes in default mode/hippocampal-frontal network and executive-control and cortico-limbic circuitry will be associated with decline in episodic memory and executive function.

Exploratory Aim 1: We will explore the role of treatment-resistance or poor response to the intervention in predicting cognitive outcomes.

Exploratory Aim 2: We will follow a subset of participants (those recruited within 2 years of the initial evaluation) to assess clinical trajectory of mood and cognitive symptoms with 24-month follow-up.

Exploratory aim 3: We will explore the difference in changes in gene expression and peripheral pro-inflammatory cytokines associated with clinical response to the interventions. To use peripheral blood to conduct transcriptome profiling with the same R01 protocols to identify gene expression and peripheral inflammatory biomarkers correlates of clinical response to TCC versus HEW.

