Exploratory Hypothesis 3: Treatment response to TCC or HEW will be associated with changes in expression of inflammation, neuroplasticity-related genes and peripheral biomarkers (e.g. cytokines, telomerase), and baseline levels of these genes and cytokines will predict future clinical response.

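### The only RNA method in the plan is the genomic-DNA sentence repeated, so the gene-expression part of Exploratory Aim 3 has no written RNA isolation or quality step

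*Combined protocol and SAP*

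**What the plan says.** Section 1.2 sets the aim: "To use peripheral blood to conduct transcriptome profiling with the same R01 protocols to identify gene expression and peripheral inflammatory biomarkers correlates of clinical response". Exploratory Hypothesis 3, which follows it, reads in part: "Treatment response to TCC or HEW will be associated with changes in expression of inflammation, neuroplasticity-related genes and peripheral biomarkers". It goes on to say that baseline levels will predict later response.

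Section 6.2.1 gives the sampling: "Blood samples will be collected for the RNA and telomerase analyses at screening (visits 1-3) and 12 weeks post-randomization (or early termination"). It then says: "A sample of 10ml of blood will be collected and it will be processed by the Core Laboratories of UCLA Department of Human Genetics".

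The laboratory methods come later in Section 6.2.1, under blood samples and peripheral biomarkers. The paragraph headed for DNA and gene expression says: "Genomic DNA will be extracted from whole blood and isolated using a Wizard Genomics DNA Purification Kit". The next paragraph, headed for RNA and microarray analyses, says: "RNA will be extracted from whole blood and isolated using a Wizard Genomics DNA Purification Kit". Both sentences end with the same 0.7% agarose gel step, the same citation and the same reference to a standard protocol. Participation in the genetic portion is described as voluntary.

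Section 9.5.2 lists change in gene expression among the exploratory outcomes. Section 9.6 compares that change between arms and correlates it with change in depression and cognitive scores, under the label Exploratory aim 1.

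**The concern.** A microarray study of expression needs RNA. The one RNA procedure the plan states names a kit for purifying DNA, in a sentence that already serves for DNA. Someone working from this document alone would follow a procedure written for another analyte. They would also have no criterion for deciding whether a sample is good enough to array.

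Both parts of Exploratory Hypothesis 3 are exposed. Change in expression needs usable RNA at screening and at week 12, and baseline prediction needs it at screening. The between-arm comparison in Section 9.6 uses the same measurements. If the written procedure differs from what the laboratory does, the document cannot serve as the record of how the exploratory data were generated.

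**Working it through.** No sample-size, power or error-rate figure is involved, so the check is a comparison of texts, followed by a bound on how many samples are concerned.

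**Step 1: the two method sentences side by side (Section 6.2.1).**

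| Element | DNA paragraph | RNA paragraph |
|---|---|---|
| Subject | Genomic DNA | RNA |
| Source | Whole blood | Whole blood |
| Kit | Wizard Genomics DNA kit | Wizard Genomics DNA kit |
| Check | 0.7% agarose gel | 0.7% agarose gel |
| Citation | Same | Same |

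An exact string comparison, with the subject replaced by a placeholder in each sentence, finds the two identical. The sentences have 38 and 37 words, and the one-word difference is the subject. That the kit is for DNA is taken from its name as printed; nothing here relies on outside knowledge of its chemistry.

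**Step 2: is an RNA method given anywhere else?**

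- Section 1.2 names transcriptome profiling and refers to R01 protocols that are not among the documents.
- Section 6 mentions blood for routine tests and genetic analysis, processed at the clinical and translational research center. It gives no RNA step.
- Section 6.2.1, in the earlier blood-sample paragraph, gives timing, a 10 ml volume and a core laboratory. It gives no isolation method.
- Section 6.2.1, in the telomerase and NFκB paragraph, assigns 10 ml to one heparin tube for those assays. It assigns no tube or aliquot to RNA.
- Sections 9.5.2 and 9.6 name the outcome and the comparisons only.
- Appendix A has a single combined row for fMRI and blood draw, with no analyte named.
- The work cited for the gel step does not appear in the Section 14 reference list, so the standard protocol cannot be traced from there.

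The documents therefore contain no RNA-specific isolation step, no RNA quality check, no array platform and no expression processing.

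**Step 3: how far it reaches.**

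- Ceiling: 220 randomized × 2 RNA time points (screening and week 12) = 440 samples, if everyone opts in and gives both.
- Planned completers: Section 4's preceding population text gives 99 per arm at week 12 (110 × 0.9 = 99), so 2 × 99 = 198 completer pairs if all opt in. Early-termination draws could add pairs.
- The opt-in rate is not stated, so the expected number lies somewhere below these figures and cannot be narrowed.

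Appendix A also marks the combined row at the last follow-up, but the text names RNA only at screening and week 12, so only those two are counted.

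**Step 4: related labels.** The paragraph headed for DNA and gene expression describes only genomic DNA. The gene-expression work is Exploratory Aim 3 in Section 1.2 but Exploratory aim 1 in Section 9.6. In Section 1.2 the number 1 belongs to treatment resistance and poor response as predictors of cognitive outcomes.

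**The case against.** The strongest reply is that this is a duplicated sentence in a summary paragraph and not the operating laboratory procedure. Section 1.2 says the profiling will follow R01 protocols, and Section 6.2.1 sends the blood to a human genetics core laboratory. Either may hold a proper RNA procedure. The sentence itself defers to a standard protocol. The work is exploratory, carries no power calculation and supports no confirmatory test.

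Much of this stands. The slip explanation is the most likely one, and the scope is narrow. But pointing to a protocol that is not supplied does not cancel a method that is stated. The text affirmatively names a kit and a check for RNA, and both belong to DNA. This is more than a detail left to the laboratory.

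A reader might infer several stronger things that the documents do not support:

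- **That the transcriptome work cannot be done.** The text shows what is written, not what the laboratory does.
- **That baseline samples will be lost for good.** The documents do not say whether RNA blood is banked, split or processed at once, so irreversibility cannot be established.
- **That 440 samples are at risk.** That is a ceiling at full opt-in and full attendance, and it assumes the sentence is followed literally for every sample.
- **That assay batches must be balanced by arm and paired by time point.** This is sensible practice, particularly because classes of 6 or 7 are randomized together, but it is optional and separate from the copied sentence.

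**Conclusion.** The RNA paragraph in Section 6.2.1 is wrong as written. It repeats the DNA method, and no other section supplies an RNA isolation or quality step for the gene-expression part of Exploratory Aim 3. This rests on the exact match of the two sentences and on the absence of any other RNA procedure in the documents supplied.

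The size is limited. It concerns participants who opt in, with an upper bound of 220 people at two time points and an unknown expected number. The HAMD primary outcome, the imaging outcomes, and the cytokine, telomerase and NFκB measurements do not depend on the sentence.

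The conclusion is about the written plan. Whether actual processing is affected depends on the R01 protocols and the core laboratory's practice, which cannot be seen here.

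**What to change.** 1. In Section 6.2.1, replace the RNA sentence with the collection, isolation and quality-control procedure actually used for RNA, including the quality threshold a sample must pass before it is arrayed. Alternatively, cite the specific R01 protocol that contains these steps.
2. Confirm with the processing laboratory that samples are handled that way, including any already collected.
3. Change the heading of the DNA paragraph so that it matches its content, which is genomic DNA only.
4. Reconcile the aim number between Sections 1.2 and 9.6.

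If the laboratory already follows an RNA procedure, the cost is a few sentences and one confirmation. If it has been following the printed text, there is also the cost of changing consumables and handling from that point on. Batch balancing may be added if the team wishes, but it is not needed to correct this error.
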